13.1.2 Study Drug Supply

The Sponsor will provide MT-7117 and placebo tablets in aluminum/aluminum blister wallets to each site, for each subject, for the duration of their participation in the study. The IWRS will allocate sufficient uniquely numbered, blinded blister wallets, to be dispensed by the Investigator, study nurse or hospital pharmacist, according to the subject's randomized treatment group (MT-7117 300 mg or placebo) and study visits. Where down titration is required the IWRS will allocate the dose accordingly.

Subjects will be instructed to bring their study drug with them to each visit. Subjects will return all study drug that may remain in their possession to the study staff at the EOT visit. In cases where subjects forget to return to the clinical site with their blister wallets suitable for all treatment groups (placebo, 300 mg, 200 mg, and 100 mg), sites will be instructed to inquire as to the subjects daily dosing compliance, capturing total number of days missed. Subjects will be instructed to return study drug packaging at the follow up visit.

13.1.3 Formulation, Packaging, Site Storage, and Labeling (MT-7117)

Study drug tablets will be provided in 2 strengths: 0 mg (placebo) and 100 mg (MT-7117) tablets. Study drug will be provided to the study sites in labeled blister wallets. All study drug should be stored according to the study drug clinical label.

Required study site documentation for MT-7117 tablets will include, but may not be limited to, the following information:

- Receipt date
- Description of study drug package, and study drug product
- Lot number or code/Batch number or code
- Expiration and manufacturing dates

- Dispensing information
- IND number
- Certificate of Compliance

13.1.4 Certificate of Compliance Shipping, Receipt, Handling and Storage

On receiving a shipment of finished study drug at the Investigator site, the Investigator or designee will conduct an inventory check and complete a supplies-receipt document, the original of which will be retained at the Investigator site. In addition, a copy must be returned to the Sponsor or designee. The Investigator or designee will maintain a record of all study drug received and returned.

Study drug at the Investigator site will be stored according to the conditions stated on the study drug clinical label in a locked, restricted-access area. A temperature log recording the daily continuous temperature of the storage area will be maintained (including weekends). Any study drug storage temperature deviations will be reported to the Sponsor as soon as possible.

13.1.5 Dispensing

At each visit, the Investigator or designee will provide the subject with the allocated dose. A record of the study drug dispensed to each subject will be maintained by the Investigator or designee in an Investigational Product Accountability Log. Dispensed study drug will not be re-allocated to a subject.

In the cases where a subject encounters a missed visit that renders a subject without sufficient study drug to maintain daily dosing (e.g., a subject resides out of state relative to the Investigator's location and experiences a travel conflict), the site may ship additional wallet to the subject upon written Sponsor approval, the site may ship additional study drug until the subject can make the next scheduled visit to the clinical site to the subject. In these instances, the Sponsor (and/or the Clinical Research Organization designee) will assist the site to ensure the process is documented appropriately. Shipments made in these rare instances will require that study drug be maintained within the required temperature range along with confirmation of receipt by the study subject. This process will not be allowed where site policies prohibit it. Subjects should return to the clinical site to complete the scheduled visit and carry out the required assessment and dispensation of study drug.

13.1.6 Study Drug Accountability

The Investigator or designee must maintain an accurate record of the shipment and dispensing of study drug in an Investigational Product Accountability Log. Study drug accountability will be noted by the field monitor during site visits and at the completion of the study. Subjects will be asked to return all unused study drug and packaging on a regular basis, at the end of the study or at the time of study treatment discontinuation.

13.1.7 Disposal and Destruction

At study close-out, and as appropriate during the course of the study and only once full accountability has taken place, the Investigator will return all used and unused study drug, packaging, study drug labels, and a copy of the completed Investigational Product Accountability Log to the Sponsor's designated monitor or to the address provided in the Investigator Binder at each site.

The study drug supply may be destroyed at the designated Sponsor facility or third party, only once authorization to destroy has been provided by the Sponsor. Site with documented drug destruction procedures and facilities may destroy drug on site only once authorization to destroy has been given by the Sponsor.

13.2 Dosing of MT-7117 or Placebo

Subjects are to self-administer the study drug 3 tablets once daily in the morning with or without food.

MT-7117 and/or placebo tablets should be swallowed whole with approximately 240 mL of water (subjects may drink an additional 240 mL of water if they have difficulty swallowing the tablets). The tablets are not to be chewed, crushed, or divided.

13.3 Treatment Compliance

The prescribed dosage, timing, and mode of administration of study drug will not be changed. Subjects will be asked questions regarding the compliance, any departures from the intended regimen will be recorded in the eCRF.

Study drug accountability and subject compliance will be documented throughout the double-blind treatment period using study-specific study drug dispensing and return record forms. For subjects who do not return their blister wallets, the site will question each to determine compliance (e.g. number of doses missed since the last visit).

Subjects will be asked to return all unused medication including empty and partially used wallets. Study drug dispensed at the previous visit will be retrieved by the Investigator or designee and compliance assessed by returned medication count.

Non-compliance will be defined as taking $\leq 80\%$ or $\geq 120\%$ of study drug during any evaluation period (from any visit to the following visit).

13.4 Subject Identification

Each subject will be assigned a unique subject number at the screening visit. At randomization, each subject will receive a unique randomization number. Both the subject number and the randomization number will be documented in the subject's source documents. The subject number will be used to identify subjects in the study.

A list identifying the subjects by their subject number will be kept at the Investigator site. The randomization numbers will be stored in the IWRS database until the database lock.

13.5 Procedures for Assigning Subjects to Treatment Groups

Randomization will take place after reconfirmation of inclusion/exclusion criteria before the first administration of study drug on Day 1 of the double-blind treatment period. Subjects will be randomly allocated on a 1:1 basis to 1 of 2 treatments (active or placebo) (Section 8.1). Subjects will be randomized via IWRS.

[REDACTED]

13.6 Maintenance of the Study Blind and Unblinding

All study treatments will be double-blinded during the 52 weeks study; neither the subject nor the study site personnel will know which treatment is being taken. Each subject's treatment will

be provided a unique code number, traceable to the identity, dose, and batch number of the study drug. The IWRS will be used to hold treatment codes for each subject. The codes will only be accessible to authorized IWRS users.

Subjects down-titration will be processed via IWRS. Subjects in the MT-7117 300 mg treatment group will be assigned to the MT-7117 200 mg treatment by IWRS. Subjects in the MT-7117 200 mg treatment group will be assigned to the MT-7117 100 mg treatment group for the second time for down-titration. Subjects in the placebo treatment group will remain in the placebo group by IWRS.

The IWRS should not normally be accessed with a request to break the treatment code for reasons other than safety or in an emergency. Should the Investigator wish to break the code for such reasons, he/she are advised to consult the Sponsor (or designee) in advance where feasible. If this is not possible, the Investigator may access the IWRS to obtain the treatment code and provide the system with the reason for breaking the blind. The Sponsor should be notified as soon as possible thereafter. If the blind is broken for any individual subject, the subject must be withdrawn from the study, and any procedures accompanying withdrawal will be performed (Section 9.5).

The Sponsor and study team will remain blinded throughout the entire duration of the study.

An electronic list of randomization codes will be retrieved from IWRS and transferred to the Sponsor at the end of the study.

As PK analysis will only be performed on samples from subjects receiving active study drug, unblinded randomization codes will be provided to the PK laboratory.

Since melanin density values could potentially be unblinding, adequate measures will be taken to protect the spectrophotometry data from disclosure to the Sponsor and the study team until the end of the study. Melanin density component data will be measured by the dedicated site staff who is not involved in routine blinded assessment of the subject, securely uploaded to and processed by the dedicated independent data management team member. The data handling procedure for melanin density will be described in the study specific procedure for melanin density endpoint posting process and data management plan.

MT-7117 and placebo tablets will be physically identical in appearance and will be packaged identically and suitably labeled to maintain the blind for the 52-week double-blind treatment period.

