9.5 Withdrawal from the Study and/or Treatment

A subject will be withdrawn from the study if ANY of the following criteria are met:

1. The subject requests to voluntarily withdraw from further participation in study.
2. The subject is significantly noncompliant with the protocol.
3. A female subject becomes pregnant while on the study.
4. Continuing in the study would be detrimental to the subject's safety in the opinion of the Investigator, for example:
 - a. The subject experiences intolerable AEs, SAEs, or adverse events of special interest (AESIs).
 - b. The subject has clinically significant changes in safety parameters at any of the postdose time points, as confirmed with a repeat assessment performed as soon as possible after the initial out-of-range result.
 - c. The subject experiences any clinically significant adverse findings from postbaseline nevi (Melanocytic Lesions) evaluation and adverse change is demonstrated histologically and confirmed by central pathologist. Visual evaluation of change will not be acceptable criteria for permanent discharge from treatment (Section 12.4).
 - d. Development of any clinically significant liver abnormalities defined as follows:

- ALT or AST $> 8 \times$ ULN.
- ALT or AST $> 5 \times$ ULN for more than 2 weeks.
- Elevated total bilirubin $> 2 \times$ ULN and ALT or AST $> 3 \times$ ULN or
- Symptoms consistent with liver dysfunction (e.g., fatigue, nausea, vomiting, abdominal pain or tenderness, fever, rash, eosinophilia $> 5\%$) with concomitant ALT or AST values $> 3 \times$ ULN.

Subjects meeting the laboratory criteria of ALT/AST and total bilirubin defined above (with or without alternative etiology), regardless of whether clinically significant or not, should be reported as a hepatic AESI (Section 14.3). The Investigator should discuss with the Sponsor Medical Monitor about the determination of etiology and the potential of interruption or withdrawal from study drug.

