In the case of an increase of ALT or AST $> 3 \times$ ULN, it is preferable to be followed by repeat testing within 48 to 72 hours of at least four of the usual serum measures (ALT, AST, ALP, and total bilirubin) at local or central laboratory to confirm the abnormalities and to determine if they are increasing or decreasing. In addition, repeat laboratory testing can include albumin, CK, direct and indirect bilirubin, GGT, and PT/INR. There also should be inquiry made about symptoms. A detailed history including but not limited to the following formations, such as symptoms, prior or concurrent disease, concomitant drugs (including nonprescription medications, herbal and dietary supplement preparations), alcohol use, recreational drug use, exposure to environmental chemical agents, should be collected. Further testing for acute hepatitis A, B, C, D, and E infection, autoimmune biomarkers and liver imaging (e.g., biliary tract) may be warranted.

Any other laboratory or clinical abnormality that the Sponsor Medical Monitor and/or Investigator considered as clinically significant should be considered as a potential reason for interruption (see Section 10.1.3.3) or withdrawal from study drug. Subjects who have withdrawn from study drug may remain in the study and be followed per protocol (Section 14.6). In addition, a subject may be withdrawn from study drug at any time for reason(s) other than those listed here. Subjects who have withdrawn from study drug cannot resume study drug.

Subjects who prematurely discontinue study treatment (withdraw from study drug) before the EOT should be encouraged to remain in the study and complete all the required study assessments and procedures through Week 52 based on the Investigator's discretion.

If a subject decides to permanently withdraw consent from the study, every attempt should be made to have the subject complete the ET visit and perform the assessments listed at Week 52 for the collection and source documentation of safety information such as AEs, dosing compliance, and review concomitant medications and date of last dose of study drug. Return of unused medication will be performed by courier where allowed.

PK blood samples are not required for subjects who have withdrawn from study drug and their last dose is ≥ 7 days before the next time point of a PK blood sample collection.

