10.1.4 End of Treatment/Early Termination

The EOT/ET visit will occur at Week 52.

If a subject is permanently discontinued from the study, every attempt should be made to have the subject complete the ET assessments as described in Table 1. In the event a subject does not return to the clinical site for the ET visit, the Investigator must make every effort to contact the subject by telephone to discuss AEs, dosing compliance, and review concomitant medications, and the date of the last dose of study drug. In these cases, the collected information (AEs, concomitant medications, date of last dose of medication, etc.) via telephone will be documented in the site source documents and eCRF. Return of unused study drug and any other materials will be performed by courier where allowed.

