5.2 Intent-to-Treatment (ITT) Population

The Intent to treat (ITT) population includes all randomized subjects who receive at least 1 dose of study drug. The ITT population will be used for all efficacy analyses. The subject randomized treatment will be used for efficacy analyses.

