7.2 Analysis Visit Definitions

Table 3 Analysis Visit Window for PtGA, PhGA, mRSS, FVC, DLco, HAQ-DI

Visit Number	Analysis Visit	Nominal day	Analysis Visit Window
1	Screening	NA	NA to -1
2	Baseline	First dose day	NA
3	Week 2	Day 15	Day 2 to 29
4	Week 6	Day 43	Day 30 to 77
5	Week 16	Day 113	Day 78 to 147
6	Week 26	Day 183	Day 148 to 228
7	Week 39	Day 274	Day 229 to 319
8	Week 52 (EOT)	Day 365	Day 320 to 379
10	Week 56 (EOS/FU)	Day 393	Day 380 to 400

Table 3 Analysis Visit Window for other than PtGA, PhGA, mRSS, FVC, DLco, HAQ-DI and pregnancy test

Visit Number	Analysis Visit	Nominal day	Analysis Visit Window
1	Screening	NA	NA to -1

2	Baseline	First dose day	NA
3	Week 2	Day 15	Day 2 to 29
4	Week 6	Day 43	Day 30 to 77
5	Week 16	Day 113	Day 78 to 147
6	Week 26	Day 183	Day 148 to 228
7	Week 39	Day 274	Day 229 to 319
8	Week 52 (EOT)	Day 365	Day 320 to 379
9	Early termination (ET)	End of treatment	End of treatment + 7
10	Week 56 (EOS/FU)	Day 393	Day 380 to 400

Table 4 Analysis Visit Window for pregnancy test

Visit Number	Analysis Visit	Nominal day	Analysis Visit Window
1	Screening	NA	NA to -1
2	Baseline	First dose day	NA
3	Week 2	Day 15	Day 2 to 29
4	Week 6	Day 43	Day 30 to 77
5	Week 16	Day 113	Day 78 to 147
6	Week 26	Day 183	Day 148 to 204
	Week 32	Day 225	Day 205 to 249
7	Week 39	Day 274	Day 250 to 294
	Week 45	Day 316	Day 295 to 340
8	Week 52 (EOT)	Day 365	Day 341 to 379
9	Early termination (ET)	End of treatment	End of treatment + 7
10	Week 56 (EOS/FU)	Day 393	Day 380 to 400

The date of the first dose of study drug is defined as Day 1.

Unless otherwise specified, the baseline value will be the last observed value of the parameter of interest prior to the first intake of study drug (this includes unscheduled visits). For FVC, %pFVC and %pDLco etc in the pulmonary function test, the baseline value will be the last observed value prior to the first intake of study drug. The data of "accepted" or "failed" generated by the centralized over read specialist will be utilized for each pulmonary function test parameters. The data accepted by the centralized over read specialist will be used if it

exists. However, when there is no accepted data available at a visit, the failed data that will be approved in BDRM will also be used.

Unless otherwise specified, no data imputation will be performed using data from outside the allowable range.

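### Protocol 13.6 and 9.5 item 2 end study participation rather than study drug alone, so after an early exit the Week 52 CRISS score is not collected and is imputed as missing at random

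*Protocol*

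**What the plan says.** Two rules take a subject out of the study altogether.

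- Protocol 13.6, on code breaks: "If the blind is broken for any individual subject, the subject must be withdrawn from the study". The same section says that the code should not normally be broken except for safety or in an emergency.
- Protocol 9.5 opens its list with "A subject will be withdrawn from the study if ANY of the following criteria are met". Item 2 of the list is "The subject is significantly noncompliant with the protocol". It gives no threshold.

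The protocol knows the alternative. Further down in 9.5: "Subjects who have withdrawn from study drug may remain in the study and be followed per protocol". Both 8.1 and 9.5 ask that subjects who stop treatment early be encouraged to go on with assessments through Week 52.

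For subjects who leave the study, 10.1.4 provides a single early-termination (ET) visit: "every attempt should be made to have the subject complete the ET assessments as described in Table 1".

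In the SAP, 5.2 defines the population: "The Intent to treat (ITT) population includes all randomized subjects who receive at least 1 dose of study drug". It adds: "The ITT population will be used for all efficacy analyses". The window table in SAP 7.2 for mRSS, FVC, HAQ-DI and the two global assessments sets Week 52 as Day 320 to 379 and has no ET row, although the table for most other assessments has one. Also in 7.2: "Unless otherwise specified, no data imputation will be performed using data from outside the allowable range". SAP 8.2.1 fills a missing Week 52 score by multiple imputation under MAR, with 50 datasets.

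**The concern.** The primary analysis is meant to be by intention to treat, but these two rules stop outcome collection in subjects who have not withdrawn consent. The gap is then filled on the assumption that, given arm, stratum and earlier scores, subjects who leave resemble those who stay.

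For code breaks that assumption is doubtful, because the usual reason for a break is a safety problem. New renal crisis, left ventricular failure and pulmonary arterial hypertension illustrate this. Each sets the CRISS score to 0.0 in Step 1 (SAP 7.1.2.1), and each could plausibly prompt a code break. The same section makes the score missing when the Step 1 entry is missing. On the readable text, such a subject who leaves before Day 320 could therefore carry an imputed Week 52 score in place of 0.

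For noncompliance there is no documented reason to expect bias in one direction, but outcomes are still lost through a rule and not through the subject's choice. At stake are the completeness of the primary endpoint and a possible small bias in the treatment difference.

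**Working it through.** **1. The chain in the text.**

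- Code break or significant noncompliance leads to study exit (Protocol 13.6; 9.5 item 2).
- After exit there is one ET visit and no further efficacy visits (10.1.4).
- An ET visit on Day 320 to 379 counts as Week 52. An earlier one falls into an earlier window, for example Week 39 if on Day 229 to 319 (SAP 7.2).
- CRISS is reported only from Week 16 (SAP 9.3), whose window opens on Day 78. A subject who leaves before then has no reported CRISS score to inform the imputation.
- The subject remains in ITT and the Week 52 score is imputed. The readable inputs are treatment group, randomisation stratum and CRISS at the visits (SAP 8.2.1). Reason for exit is not among them, but part of that text is redacted.
- The per-protocol analysis and the analysis without post-rescue data use the same method, so neither tests MAR.

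**2. The plan's own figure.** Inputs from Protocol 16.1: 36 per arm, difference 0.35, SD 0.5, two-sided alpha 0.05, 80% power, Wilcoxon-Mann-Whitney test.

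- Standardised shift: 0.35/0.5 = 0.7. Under normality P(X>Y) = Φ(0.7/√2) = 0.690.
- Noether formula: N = (1.960 + 0.842)² / [12 × 0.25 × (0.690 − 0.5)²] = 72.7 (unrounded probability), against the stated 72.
- Noncentral t with 36 × 3/π effective subjects per arm: 81.6%. Simulated Wilcoxon test: 81.2%.

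The stated 80% reproduces and is not in question.

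**3. Power if outcomes are lost.** The documents give no count, so the losses are assumed. With the same t calculation on observed subjects only:

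| Lost per arm | 0 | 1 | 2 | 3 | 4 | 6 |
|---|---|---|---|---|---|---|
| Power | 81.6% | 80.5% | 79.3% | 78.1% | 76.8% | 74.0% |

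The sample-size text makes no allowance for dropout. Observed-only power is a rough guide, since earlier visits recover some information.

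**4. Bias.** Let k be the number of affected subjects in an arm and g the average amount by which the imputed score exceeds the true one. The mean difference is overstated by

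(k_active × g_active − k_placebo × g_placebo) / 36.

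With no placebo losses and g assumed between 0.10 and 0.35:

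| k on MT-7117 | g = 0.10 | g = 0.20 | g = 0.35 |
|---|---|---|---|
| 1 | 0.003 | 0.006 | 0.010 |
| 2 | 0.006 | 0.011 | 0.019 |
| 4 | 0.011 | 0.022 | 0.039 |

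Per subject this is 0.8% to 2.8% of the planned 0.35. The standard error at the planned SD is 0.5 × √(2/36) = 0.118, so one subject at the largest gap moves the estimate by 0.010/0.118 = 0.08 standard errors, and four by 0.039/0.118 = 0.33. Equal losses and gaps in both arms cancel. These are shifts in means; the primary estimate is Hodges-Lehmann, so they indicate order of size only.

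**The case against.** The best case for the plan is that the primary score leans on subjective ratings, so a sponsor may reasonably not want ratings made with the code known. Code breaks should be few. The ET visit is actively sought, and earlier scores feed the imputation, so a subject already doing badly would be imputed lower. Much of this stands, and it limits the size of the problem. It does not justify the rule: unblinded ratings that are collected can be left out of an analysis, while ratings never collected cannot be put back.

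The objection also disposes of several stronger inferences that a reader might draw.

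- *That collected data are discarded.* No rule deletes anything.
- *That every code break marks a serious event.* Section 13.6 says what is normal, and a safety reason need not be a serious event.
- *That follow-up of the prompting event is cut short.* Protocol 9.5 refers unresolved events to 14.9, which follows them until they resolve or stabilise. Table 1 note a keeps a visit or call 4 weeks after the last dose.
- *That the higher event and discontinuation rates at 300 mg in 8.2.2 show the direction of bias.* Those data come from another disease and say nothing about code breaks or noncompliance.

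A fair point of scope is that 9.5 mixes study exit and treatment exit elsewhere too. Pregnancy means leaving the study in the list, but leaving treatment later in 9.5 and in 12.7 and 14.10. Those passages must also be reconciled.

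**Conclusion.** The point holds as a gap in outcome collection and in the missing-data checks. Two rules force study exit where the protocol otherwise keeps subjects under assessment. An exit before Day 320 leaves no Week 52 CRISS score, and the MAR value that replaces it is not tested by any readable analysis. For code breaks the missingness is plausibly informative; for noncompliance the direction is unknown.

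The size is probably small: 0.003 to 0.010 per affected MT-7117 subject, on the assumption that the true score lies 0.10 to 0.35 below the imputed one, and less if placebo subjects are lost too. Noncompliance could supply more cases than code breaks, since its trigger is undefined. Protocol 13.3 calls 80% or less in any one visit interval noncompliant (3 missed days in 14 gives 11/14 = 79%), but does not say that this triggers withdrawal.

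A reader might infer a bias of about a tenth of the planned effect, for example 4 × 0.30/36 = 0.033, or 9.5% of 0.35. The documents do not support that: it needs four losses on MT-7117, none on placebo, and scores that appear nowhere in the plan.

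**What to change.** 1. Reword Protocol 13.6 and 9.5 item 2 so that neither a code break nor significant noncompliance by itself ends study participation. Any decision on study drug stays with the sponsor's existing rules and is not addressed here.
2. Unless consent is withdrawn, continue all assessments to Week 52 and safety follow-up.
3. Flag unblinded subjects, with the date of the code break.
4. Add two sensitivity analyses of the primary endpoint to the SAP: one excluding ratings made after unblinding, and one departing from MAR for subjects who exit early, for example delta-adjusted or reference-based imputation. The first alone is not enough, because it recreates the missing values under the same MAR model.

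The cost is amendment wording and SAP text before database lock; the sample size does not change. The downside is a few ratings made with knowledge of treatment. These would mainly be the Physician Global Assessment, made by the Safety Assessor, and the patient-reported Patient Global Assessment and HAQ-DI. The mRSS is rated by a separate Efficacy Assessor (11.6) and FVC is centrally over-read (11.5).

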The PK data and MD data handling will be confirmed during blinded data review (BDR). PK data and MD data that are considered "invalid" will be flagged in the listing. Due to the nature of PK data and MD data, some issues may only be discovered after PK data and MD data are unblinded. Should new issues be identified post unblinding, and new data handling rules would have to be applied, a separate PK data and MD data handling document will be produced to provide detailed rationale and decision making. If there is clear evidence that PK sample handling errors, MD handling errors, or other factors are identified after data unblinding and these errors have led to unexpected erroneous data, then these erroneous data will be regarded as "invalid", full explanations will be given in the PK data and MD data handling document.

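### SAP 7.1.4 lets melanin-density values be declared invalid under rules written after unblinding, with an undefined trigger and only a written explanation as safeguard

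*Protocol*

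**What the plan says.** SAP 7.1.4 covers pharmacokinetic (PK) and MD data together. Its default is that handling is confirmed at the blinded data review, and values considered invalid "will be flagged in the listing". It then makes an exception, on the ground that "some issues may only be discovered after PK data and MD data are unblinded". The exception reads: "Should new issues be identified post unblinding, and new data handling rules would have to be applied", in which case a separate handling document will give the rationale. The condition for invalidation opens: "If there is clear evidence that PK sample handling errors, MD handling errors, or other factors are identified after data unblinding". A second requirement is joined to it, namely that "these errors have led to unexpected erroneous data". Such data are then regarded as invalid, with full explanations in that document.

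Protocol 13.6 states that MD values could be unblinding. Site staff outside the routine blinded assessments measure them. They are then "securely uploaded to and processed by the dedicated independent data management team member", and are kept from the sponsor and study team until the end of the study. The detailed procedure is deferred to a study-specific document and the data management plan, neither of which is available here.

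**The concern.** MD follows the drug's pharmacology. Protocol section 6 links activation of the target receptor to increased skin pigmentation, and protocol 8.2.2 reports pigmentation increases with a dose-dependent trend in the healthy-volunteer study. Whether a given MD value looks wrong therefore depends partly on the arm: a flat series on active drug, or a rise on placebo, attracts attention only once the arm is known. If validity is judged at that point, and invalid values are left out of the comparison, the values most likely to be questioned are those that run against a treatment difference. A written rationale makes such a decision visible but does not make it independent of treatment.

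**Working it through.** **Text comparison.**

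1. *Permission.* The blinded data review is the default and the post-unblinding route is the exception. The exception nevertheless allows new rules, not merely the application of rules already fixed.
2. *Trigger.* Clear evidence is required and the data must be erroneous. PK and MD handling errors are named, but a third category of other factors is added without definition. The sentence then calls all three errors, so the third category has no test of its own.
3. *Safeguard.* Documentation only. Nothing requires the late decision to be taken without treatment codes, and no analysis with and without the affected values is required.
4. *PK and MD differ.* PK is analysed only in active-drug samples (SAP 5.5) and the PK laboratory receives the codes by design (protocol 13.6), so late PK rules cannot distort an active-placebo contrast. Late MD rules can.
5. *Timing.* Protocol 13.6 lifts the MD shield and transfers the randomization list to the sponsor at the same named point, the end of the study. Neither document guarantees a period in which MD values are open to review while the codes are still closed.
6. *Precedent.* For lung function, SAP 7.2 uses sessions that failed central quality review only if they are approved at the blinded data review meeting.

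**The plan's own figure.** The documents give no number for MD. The only related figure is the primary sample size (SAP 3.3: difference 0.35, SD 0.5, two-sided 0.05, 80% power, Wilcoxon-Mann-Whitney). By Noether's formula:

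- p = Φ(0.35 / (0.5 × √2)) = 0.690
- N = (1.960 + 0.842)² / (3 × (0.690 − 0.5)²) = 72.7 using unrounded p; power at N = 72 is 79.6%

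The planned 72 reproduces, and nothing in this point alters it.

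**Illustration of size.** The inputs are assumptions, apart from 36 per arm: one normal value per subject with SD 1, no true MD difference, two-sided t-test at 0.05. Remove the k lowest active values and the m highest placebo values. Rejection is the share of 20,000 simulated trials with p < 0.05. Bias is the mean of the kept active values minus the mean of the kept placebo values.

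| k active / m placebo removed | Rejection | Bias (SD) |
|---|---|---|
| 0 / 0 | 5.1% | 0.00 |
| 1 / 0 | 6.4% | 0.06 |
| 2 / 0 | 8.7% | 0.11 |
| 3 / 0 | 11.7% | 0.16 |
| 1 / 1 | 9.7% | 0.12 |
| 2 / 2 | 19.4% | 0.23 |

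A separate run of 40,000 trials gave 4.9% (0/0), 6.2% (1/0), 11.6% (3/0), 9.2% (1/1) and 18.9% (2/2). Removal unrelated to the value causes no bias.

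**The case against.** The strongest reply is that this is a narrow, documented exception. Handling is settled blind by default, the late route needs clear evidence of error, and an explanation is written. Because protocol 13.6 hides MD values from the study team, it is plausible that some genuine faults surface only at the end. The unseen procedure and data management plan may already contain blinded validity checks. The size illustration selects the most contrary values by design and assumes no MD effect, which is unlikely for a drug expected to darken skin.

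Much of this stands, and it rules out several stronger readings that a reader might infer:

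- *Any surprising value can be discarded.* The SAP asks for clear evidence and erroneous data; surprise alone does not qualify.
- *Invalid values will be removed from analysis.* The readable text says only that they are flagged in the listing, and the exploratory analysis text that would cover MD is redacted.
- *The independent data manager already has the task of judging validity, so the late route is plainly unnecessary.* The protocol assigns that person processing only. That this happens during the study is inferred from the shielding, not stated.
- *Any genuine late-found error should stay in the main MD table.* Nothing in the documents requires this, and reporting both ways is enough.

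The reply does not answer the undefined category or the absence of any code-free decision. Sound separate procedures would not cancel a SAP clause that authorises later rules. The illustration's null is artificial, but the bias column does not depend on it: adding a constant to one arm leaves the effect of dropping its extreme values unchanged in SD units.

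**Conclusion.** The concern holds in limited form. SAP 7.1.4 authorises new MD rules and invalidation with treatment known, on a partly undefined trigger, for a measure that the protocol itself treats as capable of revealing the arm. This could bias the MD treatment comparison if invalid values are excluded from it, which is plausible but not stated.

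Under the assumptions above, the worst-case false-positive rate is about 6% to 12% for one to three active-arm values, and about 9% to 19% for one or two contrary values in each arm. These are upper illustrations, not forecasts. The clear-evidence condition should keep real practice well below them, and the actual MD model cannot be read.

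MD does not appear among the listed primary or secondary endpoints. A reader should not infer any effect on the ACR CRISS test, its alpha or the sample size.

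**What to change.** In SAP 7.1.4, for MD only:

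1. Fix the MD validity criteria in writing, and set the flags without treatment codes before the codes are released. The independent data manager named in protocol 13.6 is the natural person to do it. Because MD values may themselves hint at the arm, the criteria should be written before the values are reviewed.
2. Delete the undefined other-factors category from the trigger.
3. Have any MD value questioned after unblinding judged by someone without access to treatment codes. Report MD results both with and without it, labelled as a post-unblinding decision.
4. State whether invalid MD values are excluded from analysis or only flagged.

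The PK wording can stay as it is. The cost is a few lines of SAP text, an earlier check by someone already assigned to the data, and one extra MD table. The downside is that a genuine error found late still appears in one of the two tables.
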